5.5 Justification for Dose

Study RM-131-009 was a 12-week Phase 2b, randomized, double-blind, placebo-controlled, parallel group study to evaluate the safety and efficacy of relamorelin in diabetic participants with moderate to severe DG. The doses included within the study were 10 µg BID, 30 µg BID, and 100 µg BID. In general, all doses tested within RM-131-009 appeared to demonstrate meaningful reductions in overall DG symptom scores including vomiting episodes, with acceptable safety and tolerability. The frequency of vomiting episodes was reduced from baseline over the 12-week treatment period to a similar extent for participants who received the 3 doses of relamorelin tested and placebo. Based upon the observed dose response of change-from-baseline symptom scores collected daily over the course of 12 weeks using the DGSSD, the 30 µg BID,

and 100 µg BID doses demonstrated apparent maximal symptom score improvements, while the 10 µg BID dose achieved near maximal improvements. Of note, the twice-a-day regimen of relamorelin appears to be necessary for effective symptom relief; the 10 µg once daily (QD) relamorelin did not demonstrate significant improvement in symptom relief compared to placebo after 28 days of dosing in Study RM-131-004.

Review of the safety laboratory data collected in RM-131-009 revealed an apparent dose-related increase in HbA1c values. Although the variability in HbA1c response was high across all treatments, the 30 µg BID and 100 µg BID doses demonstrated apparent maximal changes in HbA1c values, while the 10 µg BID dose resulted in an approximately half-maximal increase after 12 weeks of study. Shorter durations of treatment (4 weeks) with 10 µg BID of relamorelin, as observed in Study RM-131-004, did not demonstrate this apparent increase in HbA1c in diabetic participants.

Based on the efficacy and safety data, the relamorelin dose selected for this study is 10 µg BID.

6 Study Population

Prospective approval of protocol deviations to recruitment and enrollment criteria, also known as protocol waivers or exemptions, is not permitted.

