5.0 Objectives

Key Objectives	Key Endpoints

 • To compare the efficacy of relamorelin with that of placebo in participants with DG with respect to a composite of the following core signs and symptoms of DG: 
 ○ Nausea ○ Abdominal pain ○ Postprandial fullness ○ Bloating • To compare the safety of relamorelin with that of placebo in participants with DG 	
 • Change from baseline to Week 12 in the weekly DGSSS • Change from baseline to Week 52 in weekly average DGSSS • AEs, clinical laboratory values, vital signs, ECGs, HbA1c, and anti-relamorelin antibodies
Other Objectives	Other Endpoints

 • To assess relamorelin treatment effect on individual symptoms of DG such as nausea, abdominal pain, bloating, postprandial fullness, early satiety, and vomiting frequency 	
 • Change from baseline to Week 12 and Week 52 in the following: 
 ○ Nausea ○ Abdominal pain ○ Bloating ○ Postprandial fullness ○ Early satiety ○ Vomiting frequency

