11.2 Clinical Laboratory Parameters

Clinical laboratory test values from all assessments (including those from unscheduled or repeat assessments) will be considered potentially clinically significant (PCS) if they meet either the lower-limit or higher-limit PCS criteria listed in [Table 11.2-1](#).

The number and percentage of participants who have PCS post-baseline clinical laboratory values will be tabulated by treatment group for the Double-blind Treatment Period. The percentages will be calculated relative to the number of participants with available non-PCS baseline values and at least 1 post-baseline assessment for the Double-blind Treatment Period. The numerator will be the total number of participants with available non-PCS baseline values and at least 1 PCS post-baseline value for the Double-blind Treatment Period.

[figure not shown]

Table 11.2–1. Criteria for Potentially Clinically Significant Laboratory Tests

Parameter	SI Unit	Lower Limit	Higher Limit
CHEMISTRY			
Albumin	g/L	< 0.9 * LLN	> 1.1 * ULN
Alanine Aminotransferase (ALT)	U/L	—	≥ 3 * ULN
Alkaline Phosphatase	U/L	—	≥ 3 * ULN
Aspartate Aminotransferase (AST)	U/L	—	≥ 3 * ULN
Calcium	mmol/L	< 0.9 * LLN	> 1.1 * ULN
Chloride	mmol/L	< 0.9 * LLN	> 1.1 * ULN
Cholesterol	mmol/L	—	> 1.6 * ULN
Creatinine	μmol/L	—	> 1.3 * ULN
Potassium	mmol/L	< 0.9 * LLN	> 2.0 * ULN
Glucose, Fasting	mmol/L	< 0.9 * LLN	> 2.5 * ULN
Glycohemoglobin A1C	%		Increase of ≥ 0.5%
Glycohemoglobin A1C	%		Increase of ≥ 1%
Sodium	mmol/L	< 0.9 * LLN	> 1.1 * ULN
Total Bilirubin	μmol/L	—	> 1.5 * ULN
Total Protein	g/L	< 0.9 * LLN	> 1.1 * ULN
Triglycerides, Fasting	mmol/L	—	≥ 3 * ULN
Urea (BUN)	mmol/L	—	> 1.2 * ULN
Magnesium	mmol/L	< 0.9 * LLN	> 1.1 * ULN
Bicarbonate	mmol/L	< 0.9 * LLN	> 1.1 * ULN
Phosphate	mmol/L	< 0.9 * LLN	> 1.1 * ULN
Uric Acid	μmol/L	< 0.9 * LLN	> 1.1 * ULN
HEMATOLOGY			
Basophils Absolute Cell Count	10 ⁹ /L	—	> 3 * ULN
Eosinophils Absolute Cell Count	10 ⁹ /L	—	> 3 * ULN
Hematocrit	Ratio	< 0.9 * LLN	> 1.1 * ULN
Hemoglobin	g/L	< 0.9 * LLN	> 1.1 * ULN
Lymphocytes Absolute Cell Count	10 ⁹ /L	< 0.8 * LLN	> 1.5 * ULN
MCH	PG	—	> 3 * ULN
MCHC	G/L	—	> 3 * ULN
MCV	fL	< 0.9 * LLN	> 1.1 * ULN
Monocytes Absolute Cell Count	10 ⁹ /L	—	> 3 * ULN
Neutrophils Absolute Cell Count	10 ⁹ /L	< 0.8 * LLN	> 1.5 * ULN
Platelet Count	10 ⁹ /L	< 0.5 * LLN	> 1.5 * ULN

Table 11.2–1. Criteria for Potentially Clinically Significant Laboratory Tests

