15.4 Repeated or Unscheduled Assessments of Safety Parameters

If a participant has repeated assessments before the start of double-blind treatment with investigational product, the results from the final assessment made before the date of the first dose will be used as baseline.

However, all post-baseline assessments will be used for PCS value determination, and all assessments will be presented in the data listings.

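### The SAP's only by-arm summary of HbA1c is an any-visit count, which gives neither size nor time course and rises with the number of draws

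*SAP*

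**What the plan says.** SAP 5.0 gives the key safety endpoints as "AEs, clinical laboratory values, vital signs, ECGs, HbA1c, and anti-relamorelin antibodies", so HbA1c is named apart from the general laboratory values. Protocol 10.3.3 does the same: it lists HbA1c as a study-specific assessment and leaves the form of the summary to the SAP.

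The SAP has no HbA1c section. HbA1c appears by arm only in the potentially clinically significant (PCS) table of SAP 11.2: "The number and percentage of participants who have PCS post-baseline clinical laboratory values will be tabulated by treatment group". Table 11.2-1 gives it two rows, "Increase of ≥ 0.5" and "Increase of ≥ 1", both in percent. A participant enters the numerator with "at least 1 PCS post-baseline value for the Double-blind Treatment Period", and the denominator requires a non-PCS baseline value. Unscheduled and repeat draws count; SAP 15.4 confirms that "all post-baseline assessments will be used for PCS value determination". Otherwise HbA1c values go to data listings.

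On the prior signal, Protocol 5.5 reports an apparent dose-related rise in HbA1c in the Phase 2b study and says that "the 10 µg BID dose resulted in an approximately half-maximal increase after 12 weeks of study". Protocol 3.3 names poorer glycemic control as a potential risk.

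**The concern.** The safety question for HbA1c is how far it moves on this dose relative to placebo, and whether a shift seen at 12 weeks persists or grows with longer treatment. An any-visit threshold count answers neither part. It does not distinguish a rise of 0.5 from one of 0.9, or week 12 from week 52.

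The count also depends on how often HbA1c was measured, because each extra draw is another chance to cross the line. The study was terminated on a calendar date (SAP 4.0), so participants will have been followed for different lengths of time. A given percentage then mixes drug effect, ordinary fluctuation and number of draws, and the reader has no table with which to separate them. At stake is whether this placebo-controlled long-term study reports the size of the one laboratory shift that the programme already had reason to expect.

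**Working it through.** **1. Figure to reproduce.** There is none. The documents give no HbA1c SD, expected rate or precision, and no HbA1c test is planned.

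**2. Inputs.**
- From SAP 11.2 and 15.4: cut-offs c = 0.5 and 1.0, read as absolute percentage points (an assumption, see step 6); any-visit rule; all draws count.
- Assumed: within-person SD of one HbA1c value s = 0.15 to 0.7 points (Protocol 5.5 says only that variability was high); k = 1, 3 or 5 post-baseline draws (the schedule table is not shown); true shift δ = 0 or 0.25 points (Protocol 5.5 gives no size in HbA1c units); independent normal measurements.

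**3. Formula.** With baseline deviation b, the share with at least one rise of c or more is

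P(k) = ∫ [φ(b/s)/s] · [1 − Φ((c + b − δ)/s)^k] db.

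For one draw this reduces to 1 − Φ((c − δ)/(s√2)). With c = 0.5, s = 0.3, δ = 0: 0.5/(0.3 × 1.414) = 1.18, and 1 − Φ(1.18) = 11.9%.

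With no true change (δ = 0):

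| s | ≥ 0.5, k = 1 / 3 / 5 | ≥ 1, k = 1 / 3 / 5 |
|---|---|---|
| 0.15 | 0.9 / 2.4 / 3.7% | about 0 |
| 0.3 | 11.9 / 25.4 / 33.5% | 0.9 / 2.4 / 3.7% |
| 0.5 | 24.0 / 44.8 / 55.1% | 7.9 / 17.7 / 24.2% |
| 0.7 | 30.7 / 53.9 / 64.3% | 15.6 / 31.8 / 40.9% |

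The count grows with the number of draws wherever it is not close to zero. As an illustration only, arms averaging 3 and 5 draws would show 25.4% against 33.5% at s = 0.3 with no drug effect, and 2.4% against 3.7% at s = 0.15.

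**4. How much of the count is background.** Take δ = 0.25 and k = 3, and divide the no-shift share by the shifted share. At s = 0.3 and c = 0.5 this is 25.4/50.1 = 51%.

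| s | ≥ 0.5 | ≥ 1 |
|---|---|---|
| 0.15 | 10% | 1% |
| 0.3 | 51% | 26% |
| 0.5 | 74% | 59% |
| 0.7 | 83% | 75% |

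The answer turns on an SD that the documents do not give, and it is always lower for the ≥ 1 row.

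**5. Can the count still separate the arms?** Yes, with equal draws. Power at two-sided 5%, with the planned 400 and 200 and δ = 0.25, serves here only as a measure of separation. At s = 0.5 it is 98% for mean change at one visit, against 96% (≥ 0.5) and 91% (≥ 1) for the count at k = 3. At s = 0.7 it is 83% against 75% and 72%.

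The mean change adds a size. Its expected value is zero under no true change, however many draws there are. The 95% CI half-width at one visit is 1.96 × s√2 × √(1/200 + 1/400) = 0.24s. That is 0.04 at s = 0.15 and 0.17 at s = 0.7. With the 200 and 100 expected completers it is 0.34s, or 0.05 to 0.24. The number actually randomized is not given, so the real precision may be worse.

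**6. Can the rows be programmed as written?** Not literally.
- A rise from baseline is not a property of the baseline value, so a non-PCS baseline is undefined for these two rows.
- HbA1c is itself measured in percent, so a percent increase can be read as absolute or relative. At the de novo entry ceiling of 11.0%, a relative 0.5% rise is 11.0 × 0.005 = 0.055 points, about one ninth of the absolute reading.

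**The case against.** The strongest reply is scope. The study was terminated, SAP 13.0 says the original primary objectives no longer apply, and SAP 16.0 cuts the plan down on purpose; even key efficacy is descriptive only. Protocol 10.3.3 allows categorical summaries and leaves the definition to the SAP, so the PCS count does not contradict the protocol. This stands: there is no breach. It does not remove the gap, because this SAP amendment added descriptive efficacy summaries for results posting, and a descriptive HbA1c table is of the same kind.

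The count also has merits. Two cut-offs are better than one. Adjustment of diabetes medication during the study is encouraged, which can pull later means back, whereas an any-visit count keeps the excursions. Leaving falls out is reasonable in a screen for worsening. Fasting glucose has its own PCS row and glycemic events enter the adverse-event tables. All of this supports keeping the count, though not as the sole by-arm summary.

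A reader might infer three stronger things that the documents do not support:
- That the count is largely noise. This needs a within-person SD that is not given; step 4 runs from 1% to 83%.
- That it is biased between arms. The arms are randomized concurrently, so a calendar stop shortens both alike in expectation. Bias needs different follow-up or testing by arm, which is not shown. Protocol Appendix 2 permits additional tests but does not say that they follow hyperglycemia.
- That the half-maximal remark in Protocol 5.5 describes a gradual time course. It compares doses at 12 weeks.

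**Conclusion.** The point holds as a reporting gap that is cheap to close. The only by-arm output for a key safety endpoint with a prior signal gives neither the size nor the time course of the change; this is true whatever the SD. The count also rises with the number of draws. From 1 to 5 draws with no true change, the ≥ 0.5 share goes from about 12% to 34% at an assumed SD of 0.3, but only from about 1% to 4% at 0.15. These figures assume independent draws; positive correlation between later values would slow the growth. The percentages will therefore be hard to interpret after early termination, although they can still separate arms with similar follow-up. The definition of the two HbA1c rows is incomplete in any case.

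**What to change.** In SAP 11.2:

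1. Add one by-arm table of HbA1c observed value and change from baseline at each scheduled visit, using the change-from-baseline descriptives already defined in Protocol Table 10-2 (N1, mean, SD, median, minimum, maximum). A descriptive 95% CI for the between-arm difference is optional.
2. Keep the any-visit count. Beside it, show the ≥ 0.5 and ≥ 1 counts at scheduled visits and the number of HbA1c draws per arm.
3. State that the increases are absolute percentage points from baseline, and that the denominator is all participants with a baseline and at least one post-baseline HbA1c value.

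The cost is one extra table, a few added columns and two clarifying sentences in an abbreviated report. The data are already collected.

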12. Positive results on the urine drug screen at Screening (Visit -2). The sponsor may permit a participant with a positive urine drug screen (UDS) by immunoassay at Screening to continue in screening while confirmatory testing by a more specific method is carried out on an aliquot of the original urine sample. If the confirmatory test is negative, the initial positive UDS will be considered to have been a false-positive urine drug screen and the participant can continue in screening. Confirmatory testing will be done at the discretion of the sponsor and must be approved by the sponsor prior to analysis. The significance of a positive screen result for drugs prescribed for the participant (eg, barbiturates, benzodiazepines, amphetamines, but not opioids or cannabinoids) should be assessed by the Investigator as to whether their stable-dose usage is clinically appropriate, and, therefore, should not be exclusionary; use of these drugs on an as-needed basis is not allowed. See Section 6.4 for additional details regarding positive urine drug screen.
13. Currently taking opiates, or expecting to use opiates during the course of the clinical study. (see Section 7.7.1 for an exception to this prohibition)
14. Treatment with glucagon-like peptide-1 (GLP-1) agonist for at least 6 weeks prior to the start of the Run-in Period (Visit -1)
15. History of pyloric injection of botulinum toxin within 6 months of screening
16. History of gastric surgery such as fundoplication, gastrectomy, gastric pacemaker placement, vagotomy, or bariatric procedure (a history of diagnostic endoscopy is not exclusionary)
17. Randomization in any previous study in which relamorelin was a treatment
18. Estimated glomerular filtration rate (eGFR) of < 30 mL/min
19. Current enrollment in an investigational drug or device study or participation in such a study within 30 days of entry into this study
20. Allergic to, or intolerant of egg, wheat, milk, or algae, as these are components of the GEBT study meal

21. Females who are pregnant, nursing, or planning a pregnancy during the study. For females who are of childbearing potential, see [Appendix 5](#)
22. The participant has a condition or is in a situation which, in the investigator's opinion, may put the participant at significant risk, may confound the study results, or may interfere significantly with the participant's participation in the study

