10.3.3 Safety Analyses

All safety analyses will be performed on the Safety Population.

The following safety categories will be summarized as appropriate (eg, categorical or continuous descriptives, shift tables) for the safety population and will be fully defined in the SAP.

- AEs
 - Clinically significant hyperglycemia- and hypoglycemia-related events
- Clinical laboratory assessments
 - Hy's law cases
- Vital signs
- ECGs
- Study-specific assessments
 - HbA1c

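### The SAP's by-arm laboratory table leaves out worsening in fasting glucose, creatinine and urea from an already abnormal baseline; a directional baseline rule and one shift summary would close the gap cheaply.

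*SAP*

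**What the plan says.** SAP 11.2 and Table 11.2-1 set the laboratory analysis.

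- **Flag.** Values are PCS "if they meet either the lower-limit or higher-limit PCS criteria" in the table. Fasting glucose has both limits (below 0.9 × LLN, above 2.5 × ULN). Creatinine (above 1.3 × ULN) and urea (above 1.2 × ULN) have a high limit only.
- **Denominator.** "The percentages will be calculated relative to the number of participants with available non-PCS baseline values and at least 1 post-baseline assessment".
- **Numerator.** "The numerator will be the total number of participants with available non-PCS baseline values and at least 1 PCS post-baseline value".
- **HbA1c.** Two rows with no absolute limit: "Increase of ≥ 0.5" and "Increase of ≥ 1" (percentage points).

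SAP 15.4 uses all post-baseline assessments for the PCS determination and sends all assessments to listings. The visible SAP text contains no laboratory shift table and no change-from-baseline summary. Protocol 10.3.3 says that the safety categories, laboratory assessments among them, will be "summarized as appropriate (eg, categorical or continuous descriptives, shift tables" and so on, with details left to the SAP.

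For de novo participants, Protocol 6.1.2 allows a screening HbA1c up to 11.0% with diabetes of at least 5 years' duration, and Protocol 6.2.3 excludes "Estimated glomerular filtration rate (eGFR) of < 30 mL/min". eGFR is a protocol laboratory test (Table 12-1) but has no row in Table 11.2-1.

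**The concern.** A PCS table limited to participants with a non-PCS baseline answers one question: who became abnormal on treatment? It cannot answer a second one: who was already abnormal and got worse? In most trials the second group is small. Here the entry criteria admit long-standing diabetes, HbA1c up to 11.0% and eGFR down to 30, so abnormal baselines on glucose, creatinine or urea are plausible.

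The second question matters for this drug. Protocol 3.3 names worse glycaemic control, including possible ketoacidosis, as a potential risk, and Protocol 3.2 reports dose-related trends in fasting hyperglycaemia in Phase 2b. Protocol 3.3 also warns that remedial action against rising glucose might increase hypoglycaemic reactions. Under a two-sided flag, a participant who starts high and later goes low is not counted as low. That participant is a plausible candidate for exactly this sequence.

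**Working it through.** The SAP states no figure on this point, so there is none to reproduce. The check applies the SAP 11.2 rule to test cases and then asks how many participants it could affect.

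**Step 1. The rule.** Let b be the baseline and p any post-baseline value.

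- PCS(v) is true if v is below the low limit or above the high limit.
- In the denominator: PCS(b) is false and at least one p exists.
- In the numerator: in the denominator, and PCS(p) is true for at least one p.

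The limits as multiples of LLN and ULN come from Table 11.2-1. The laboratory's LLN and ULN are not in the documents; for glucose I assume 3.9 and 5.6 mmol/L. The limits are then 0.9 × 3.9 = 3.51 and 2.5 × 5.6 = 14.0 mmol/L. For an assumed ULN of 5.5 to 6.1, the high limit runs from 13.75 to 15.25.

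**Step 2. Test cases.**

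| Test | Baseline → post-baseline | Denominator | Numerator |
|---|---|---|---|
| Fasting glucose, mmol/L | 7 → 15 | yes | yes |
| Fasting glucose, mmol/L | 15 → 28 | no | no |
| Fasting glucose, mmol/L | 3.2 → 16 | no | no |
| Creatinine, × ULN | 1.29 → 1.31 | yes | yes |
| Creatinine, × ULN | 1.35 → 3.0 | no | no |
| HbA1c, % | 10.8 → 11.4 (+0.6) | yes | yes at ≥ 0.5 only |
| HbA1c, % | 10.8 → 12.0 (+1.2) | yes | yes at both |

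A creatinine rise of 0.02 × ULN across the limit counts, while a rise of 1.65 × ULN from just above it does not. The third glucose case shows the two-sided flag at work: a low baseline removes a later high value, and by the same logic a high baseline removes a later low one. Creatinine and urea have no low limit, so direction does not matter there. The HbA1c rows behave differently: a baseline value cannot meet an increase criterion, so no one leaves those rows for a high baseline. That is my reading; the SAP does not say how its baseline condition applies to them.

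**Step 3. How many.** The documents give no baseline distribution. For an assumed share f with a PCS baseline on one test, the row loses 400f relamorelin and 200f placebo participants at the planned enrolment:

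| f | Relamorelin | Placebo | Total of 600 |
|---|---|---|---|
| 5% | 20 | 10 | 30 |
| 10% | 40 | 20 | 60 |
| 20% | 80 | 40 | 120 |
| 30% | 120 | 60 | 180 |

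The study was terminated early, so the actual numbers may be smaller; the fractions are what carry over.

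**Step 4. An illustration for glucose.** Assume lognormal fasting glucose with mean 9 to 10.5 and SD 3.5 to 4.5 mmol/L, ULN 5.5 to 6.1, within-person correlation 0.4 to 0.6 (log scale), five post-baseline draws and no drug effect. Simulating 400,000 participants for each combination of the end values gives:

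- 5.5% to 19.5% above the high limit at baseline.
- Of all participants above the limit at some post-baseline draw, 15% to 37% are left out because of their baseline.
- Of those left out, 30% to 40% never exceed their own baseline. Those who do are 9% to 26% of all participants above the limit on treatment.

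With no drug effect in the model, even the last figure is ordinary fluctuation. It shows how much of the signal-bearing group the row does not see, not how much harm it hides.

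**The case against.** A reader might infer that this is the only glucose comparison in the report, and that an effect in participants with high baselines could not show in any table. The documents contradict that. The HbA1c rows in the same table keep those participants. Protocol 9.2.7.2 requires clinically significant hyper- and hypoglycaemia to be reported as adverse events, and SAP 11.1 tabulates treatment-emergent events by arm, preferred term and severity whatever the baseline. Nor is renal decline invisible: a participant with PCS creatinine stays in the urea, potassium, bicarbonate and phosphate rows unless PCS there too. This takes the exclusion as per parameter, which is the natural reading but is not stated.

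The rule is also the usual treatment-emergent definition. It conditions on a pre-treatment value, so it does not bias the randomised comparison. Protocol 10.3.3 offers shift tables as examples, not commitments. SAP 4.0 and 16.0 openly describe an abbreviated analysis after termination on 04 September 2020. The entry limits cited are de novo criteria; rollover limits sit in lead-in protocols not available here. Protocol 6.1.2 also asks for controlled and stable glucose, which it explains as no ketoacidosis, hyperosmolar episode or severe hypoglycaemia in the preceding 6 months.

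All of this stands, and it limits the point. It does not remove it, because the backstops are incomplete:

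- Protocol 9.4.4 and Appendix 4 keep laboratory findings associated with the underlying disease out of adverse event reporting unless judged more severe than expected. That judgement bears most on participants already abnormal.
- The visible SAP has no dedicated table for the hyper- and hypoglycaemia-related events that Protocol 10.3.3 lists.
- HbA1c responds slowly. Protocol 3.2 describes a slight increase after about 8 weeks, and Protocol 5.5 no apparent increase after 4 weeks at 10 µg BID. In a study cut short, brief exposures may show in fasting glucose first. HbA1c also cannot show low glucose.

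**Conclusion.** The point holds in limited form. On fasting glucose, creatinine and urea, worsening from an already-PCS baseline is in no by-arm laboratory table. On the literal rule, a PCS glucose baseline in one direction also removes the participant from the count in the other. Part of glycaemic worsening is still compared by arm through HbA1c and adverse events, and part of renal decline through other chemistry rows and adverse events.

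The loss is in description and sensitivity, not in validity. Its size is unknown; the 5% to 30% range and the simulated shares rest on my assumptions, and the documents do not show that PCS baselines were common. The conclusion also assumes that nothing in the part of SAP 11.2 not shown in the public text supplies the missing summary. This is a cheap improvement, not an error that undermines the safety analysis.

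**What to change.** In SAP 11.2:

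1. State that the baseline condition applies per parameter and per direction. Only a baseline above the high limit removes a participant from the high count, and only a baseline below the low limit removes one from the low count. Report the two counts separately where a test has both limits.
2. Keep the existing PCS row. Add a by-arm shift summary for fasting glucose and creatinine: baseline low, non-PCS or high against the worst post-baseline low and the worst post-baseline high. Include every participant with a baseline and a post-baseline value, whatever the baseline.
3. For the same participants, add by-arm change from baseline to the worst value for fasting glucose and creatinine, with eGFR. High baselines tend to fall back on repeat measurement, so read these changes between arms, not against zero.

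The cost is some SAP wording and a few extra tables in an abbreviated report. No new data are needed.
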